5.4.5 Timepoint assessment

Diary Timepoint Definitions

At Visit 3.1 (Day -1), participants on OADs or an oral or injectable GLP-1RA will be required to take their dose after the blood sample for fasting plasma glucose (FPG) and HbA1c is collected and 30 minutes before administration of the meal during the MMTT and measures for both β -cell function and PPG analyses will be captured. β -cell function (plasma glucose, insulin, and C-peptide) will be collected at baseline and only plasma glucose will be collected at week 16. Participants on a weekly GLP-1RA should have their baseline MMTT conducted within 7 (\pm 3) days after their last dose and administer their last weekly GLP-1RA dose 7 (\pm 2) days before the first dose of Soliqua 100/33. During Visit 3.1 (on the morning of Day -1, the day before the first dose of Soliqua 100/33), the last doses of daily DPP-4i and daily GLP-1RA should be

administered. Down-titration of SU dose to 50% should occur at Visit 3.2 (when starting Soliqua 100/33).

Participants are enrolled into the trial at Visit 3.2, which is considered Day 1. The first dose of Soliqua 100/33 is administered at this visit (Visit 3.2).

Visit windows

All post-baseline data (e.g. CGM data, MMTT data, patient reported outcome data, laboratory data, physical exam data, and vital signs data) will use windowing to determine the analysis visit.

The visit windows will consider nominal visits and unscheduled visits within the window. If there are two visits within a window, then the visit closest to the target day will be used.

Table 8 – Visit Windows for non-CGM data

Week	Target Day	Days
Week -4	-28	informed consent date to -15
Week -2	-15	-14 to -1
First treatment	1	1
Week 8	57	2 to 60
Week 14	99	61 – 102
Week 16	113	103 – 116

Schedule of Events

Study Period	Screening	Run-in		Treatment ^a							Follow-up
			Baseline	Titration ^b							
Visit ^c	1	2	3.1 ^d	3.2 ^{e,f}	4.0–4.6 ^g	5	5.1–5.4 ^h	6	7 ⁱ	Unscheduled ^j	8
Visit Type	Clinic	Clinic or Home	Clinic	Phone ^e	Phone	Clinic or Home	Phone	Clinic or Home	Clinic	Clinic or Home	Phone
Week	-4	-2	0	0	1 to 7	8	9 to 12	14	16		18
Day	-28	-15 ^k	-1	0	1 to 49	56	63 to 84	98	112		126
Window (Days)				7 ^(±2) ^e		±3		±3	±3		±3
Informed consent	X										
Inclusion and exclusion criteria	X		X								
Demography (including height and body weight)	X										
Medical/surgical history	X										
Current medications	X										
Physical examination	X								X		
Body weight and height ^l	X		X						X		
Dispense glucometer	X										
Fasting SMPG ^m		←-----X-----→									

Study Period	Screening	Run-in		Treatment ^a							Follow-up
			Baseline	Titration ^b							
Visit ^c	1	2	3.1 ^d	3.2 ^{e,f}	4.0–4.6 ^g	5	5.1–5.4 ^h	6	7 ⁱ	Unscheduled ^j	8
Visit Type	Clinic	Clinic or Home	Clinic	Phone ^e	Phone	Clinic or Home	Phone	Clinic or Home	Clinic	Clinic or Home	Phone
Week	-4	-2	0	0	1 to 7	8	9 to 12	14	16		18
Day	-28	-15 ^k	-1	0	1 to 49	56	63 to 84	98	112		126
Window (Days)				7(±2) ^e		±3		±3	±3		±3
HbA1c measurement ^o	X	X	X						X		
Blinded CGM device application ^o		X						X			
MMTT ^p			X						X		
CGM device removal and data download (after the MMTT) ^q			X						X		
CGM compliance assessment ^r			X						X		
MMTT-derived β -cell function (insulin, C-peptide, and plasma glucose) ^s			X						X		
MMTT PPG measures ^s									X		

Study Period	Screening	Run-in		Treatment ^a							Follow-up
			Baseline	Titration ^b							
Visit ^c	1	2	3.1 ^d	3.2 ^{e,f}	4.0–4.6 ^g	5	5.1–5.4 ^h	6	7 ⁱ	Unscheduled ^j	8
Visit Type	Clinic	Clinic or Home	Clinic	Phone ^e	Phone	Clinic or Home	Phone	Clinic or Home	Clinic	Clinic or Home	Phone
Week	-4	-2	0	0	1 to 7	8	9 to 12	14	16		18
Day	-28	-15 ^k	-1	0	1 to 49	56	63 to 84	98	112		126
Window (Days)				7(±2) ^e		±3		±3	±3		±3
Last doses of daily DPP-4i and daily GLP-1 RA (on the morning of Day - 1, the day before the first dose of Soliqua 100/33) and down-titration of SU dose to 50% (when starting Soliqua 100/33) ^l			X	X							
Dispense IMP			X			X				X	
Soliqua pen instruction ^a			X	X							
eDiary set-up	X										
eDiary completion	←-----X-----→										
Daily IMP dosing ^l	←-----X-----→										
IMP dose adjustments					X	X	X			X	
Concomitant medications			X	X	X	X	X	X	X	X	X
IMP adherence assessment						X		X	X		
FPG ^m			X					-	X		
DM-SAT ⁿ			X					-	X		

Study Period	Screening	Run-in		Treatment ^a							Follow-up
			Baseline	Titration ^b							
Visit ^c	1	2	3.1 ^d	3.2 ^{e,f}	4.0–4.6 ^g	5	5.1–5.4 ^h	6	7 ⁱ	Unscheduled ^j	8
Visit Type	Clinic	Clinic or Home	Clinic	Phone ^e	Phone	Clinic or Home	Phone	Clinic or Home	Clinic	Clinic or Home	Phone
Week	-4	-2	0	0	1 to 7	8	9 to 12	14	16		18
Day	-28	-15 ^k	-1	0	1 to 49	56	63 to 84	98	112		126
Window (Days)				7(±2) ^e		±3		±3	±3		±3
Hypoglycemia events ^g	X	X	X	X	X	X	X	X	X	X	X
Recording of AEs/SAEs (including AESIs)	X	X	X	X	X	X	X	X	X	X	X
Product complaints					X	X	X	X	X		
Vital signs (including heart rate, systolic and diastolic BP)	X		X						X		
Calcitonin	X										
Clinical chemistry	X		X						X		
Hematology	X		X						X		
Urinalysis ^g	X		X						X		
Pregnancy test ^g	X		X			X			X		

Abbreviations: ADA, American Diabetes Association; AE, adverse event; AESI, adverse event of special interest; BMI, body mass index; BP, blood pressure; CGM, continuous glucose monitoring; DM-SAT, Diabetes Medications Satisfaction Questionnaire; DPP-4i, dipeptidyl peptidase-4 inhibitor; DTP, direct-to-patient; eDiary, electronic diary; FPG, fasting plasma glucose; GLP-1RA, glucagon-like peptide-1 receptor agonist; Hb, hemoglobin; HbA1c, glycated hemoglobin; HCP, healthcare provider; IMP, investigational medicinal product; MMTT, mixed-meal tolerance test; OAD, oral antidiabetic drug; PPG, postprandial glucose; SAE, serious adverse event; SMPG, self-measured plasma glucose; SU, sulfonylurea.

^a For participants who discontinue study treatment prematurely, the visit window can be extended by 14 days to collect the CGM data, followed by MMTT data, before they permanently discontinue the treatment. Before permanent discontinuation of treatment regardless of the reason or as soon as possible after the decision for discontinuation has been made, if possible, the participant will undergo all procedures planned for the last dosing day with Soliqua 100/33 and the follow-up visit (ie, Visit 7 and above).

^b During the titration period, the dose of IMP will be adjusted upwards or downwards by 2 to 4 units every week, or at the investigator's discretion, based on the participant's blood glucose monitoring results, with the objective of safely attaining a fasting SMPG value of 80 to 100 mg/dL, as well as other glycemic goals, while minimizing the risk of hypoglycemia and hyperglycemia. The duration of the titration period and number of phone contacts to safely meet the study goals will also be at the discretion of the investigator.

- c Participants will have the choice to have Visits 2, 5, and 6 performed at the study site or at home. This choice is to be determined at the screening visit. Participants who opt for site visits should be encouraged not to change to home visits during the study period. However, if this is unavoidable, the home health provider and the sponsor-approved courier company for IMP shipment will need at least 72 hours' notice from the investigator to arrange a home visit and DTP IMP supply, if required.
- d Participants on weekly GLP-1RA should administer their last dose 7 (\pm 2) days before the first dose of Soliqua 100/33, whereas the last dose of daily DPP-4i and daily GLP-1RA (oral or injectable) should be administered on the morning of Day -1, the day before the first dose of Soliqua 100/33.
- e It is the first day of Soliqua 100/33 administration and includes a phone contact to ALL participants to ensure that all administration procedures were successfully executed and to answer any questions. The first day of Soliqua 100/33 administration (ie, Visit 3.2, Day 0) for participants on weekly GLP-1RA will depend on their administration schedule and may not be the day immediately following Visit 3.1. Soliqua 100/33 administration for these participants should be 7 (\pm 2) days after their last weekly GLP-1RA dose. A phone contact should be made to **participants on weekly GLP-1RA on the day before Soliqua 100/33 initiation**, to remind them of the next morning's injection and to provide instructions for SoloStar pen use. The participants will provide their concomitant medication details to the site personnel over the phone.
- f Doses of SU should be down-titrated by 50% when Soliqua 100/33 is started on Day 0.
- g Weekly phone contacts for dose adjustments will be continued at the investigator's discretion until the desired fasting SMPG value is achieved.
- h If the desired fasting SMPG value is not achieved in the first 8 weeks of treatment; the investigator has the option to continue weekly dose titration phone contacts for an additional 4 weeks (until Week 12) for the purpose of achieving glycemic targets.
- i At the end of the study, participants should discuss with the investigator, in collaboration with their HCP, whether to continue on the Soliqua 100/33 treatment regimen or transition to an alternate antihyperglycemic therapy.
- j An unscheduled visit can be planned anytime during the treatment period if IMP resupply is required. This can be a site visit or via phone contact with DTP IMP delivery. If DTP Soliqua 100/33 supply is required, the sponsor-approved courier company will need at least 72 hours' notice to collect Soliqua 100/33 treatment kits from a study site.
- k Visit 2 will be performed at Day -15 for ALL participants, including those on weekly GLP-1RA, who will administer their last dose 7 (\pm 2) days before the first dose of Soliqua 100/33; those taking daily SU (dose will be down-titrated by 50% on the morning of Soliqua 100/33 initiation); and those taking daily DPP-4i, and daily GLP-1RA (oral or injectable; their last dose will be administered on the morning of Day -1, the day before the first dose of Soliqua 100/33).
- l Body weight and height will be recorded during the screening period for the calculation of BMI (metric: BMI = weight (kg)/height [m²]) and only body weight will be recorded during the baseline and at the end of the treatment period.
- m Participants are required to measure fasting SMPG values before breakfast at least 3 to 4 times per week throughout the study period (to inform each dose adjustment) and record the results in the eDiary. During the titration period, fasting SMPG should be performed on each of the 3 to 4 days before each dose adjustment.
- n HbA1c will be measured during the screening and run-in periods, and at Visit 3.1 (before administration of the meal) at the central laboratory, to determine study eligibility, and at the end of the 16-week treatment period (Visit 7), to determine change in glycemic control.
- o Blinded CGM will be performed for 14 continuous days. The baseline CGM measure will be captured before discontinuing the daily (oral or injectable) or weekly GLP-1RA, DPP-4i, or down-titration of SU by 50%, and before initiation of Soliqua 100/33 treatment. During the run-in period, CGM device reinsertion will be allowed for participants who do not meet the CGM compliance criteria. During the end of the treatment period, CGM device reinsertion will also be allowed for participants who do not meet the CGM compliance criteria.
- p The MMTT includes a standardized meal (ie, Boost Very High Calorie) that contains approximately 530 kcal and is composed of 19% carbohydrates, 44% protein, and 33% fat. The composition and the quantity of the standardized meal must be identical throughout the study period. Baseline MMTT is to be performed before discontinuation of daily (oral or injectable) or weekly GLP-1RA, DPP-4i, or down-titration of SU medications. Participants on weekly GLP-1RA should have their baseline MMTT conducted within 7 (\pm 3) days after their last dose. During the baseline (Visit 3.1), blood samples will be collected at the following time points: premeal (30 min) and just before administration of OADs or GLP-1RA (oral or injectable) (baseline); time 0 (just before meal administration); 10 min; 20 min; and 0.5, 1.0, 1.5, 2.0, 2.5, 3.0, and 4.0 hours post-meal for plasma glucose, C-peptide, and insulin levels. At Visit 3.1, participants on OADs or an oral or injectable GLP-1RA will be required to take their dose after blood sample for FPG and HbA1c is collected and 30 minutes before administration of the meal during the MMTT (during which measures for both β -cell function and PPG analyses will be captured). Soliqua 100/33 should be administered 30 minutes before administration of the meal during the MMTT at Visit 7 (during which only measures for PPG analyses will be captured). At the end of the treatment period (Visit 7), blood samples will be collected for plasma glucose levels, as follows: premeal (30 min) and just before administration of Soliqua 100/33; and time 0 (just before meal administration); 0.5, 1.0, 1.5, 2.0, 2.5, 3.0, and 4.0 hours post-meal. These values will be used for PPG analyses with the goal of deriving reduction in maximum glucose exposure in the 4-hour period after the breakfast meal after Soliqua 100/33 administration at Week 16 compared with baseline.
- q At baseline, the CGM device will be removed and the data will be downloaded on Day -1 at their next site visit (ie, Visit 3.1), after collection of C-peptide, insulin, and plasma glucose data from the MMTT. Downloaded CGM data will be reviewed by the investigator to determine participants' study eligibility. At the end of the treatment period, the CGM device will be removed and the

data will be downloaded on the fifteenth day after CGM placement (ie, Visit 7; after collection of only plasma glucose data from the MMTT). Downloaded CGM data will be verified by the investigator at the site to determine participants' study completion.

r Participants who do not meet CGM compliance criteria at baseline will be considered screen failures.

s Participants will undergo the MMTT to assess maximum PPG exposure in the 4-hour period after the breakfast meal with biomarkers of β -cell function (plasma glucose, insulin, and C-peptide) measured at Visit 3.1 (ie, site visit during the baseline period), whereas only plasma glucose will be assessed at Visit 7 (ie, end of the treatment period).

t Participants should discontinue GLP-1RA, DPP-4i, or down-titrate SU medications after all baseline assessments have been completed. SU doses should be down-titrated by 50% when starting Soliqua 100/33, whereas the last dose of daily DPP-4i and daily GLP-1RA (oral or injectable) should be administered on the morning of Day -1, the day before the first dose of Soliqua 100/33.

Participants on weekly GLP-1RA should administer their last dose 7 (\pm 2) days before the first dose of Soliqua 100/33.

u Soliqua pen instructions will be given to all participants at Visit 3.1. A phone contact should be made to **participants on weekly GLP-1RA** on the day **before Soliqua 100/33 initiation**, to remind them of the next morning's injection and to provide instructions for SoloStar pen use.

v For the scheduled site visits, participants are required to arrive fasting without administering the Soliqua 100/33 injection. Fasting is defined as no food intake in the 8 hours before blood sampling, except water.

w Baseline DM-SAT should be completed before discontinuation or down-titration of baseline therapies. The questionnaire should be completed at the start of the visit before any other study tests or procedures are performed or Soliqua 100/33 is administered.

x The following hypoglycemia categories of interest will be presented: overall hypoglycemia and confirmed hypoglycemia (ADA Levels 1, 2, and 3; Section 6.3.2).

y Urinalysis: pH, glucose, ketones, leukocytes, blood/Hb, protein.

z Only for women of childbearing potential; urine pregnancy test.

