4.4.1.2 Main analytical approach

The key secondary estimand will be estimated based on the efficacy analysis set using measurements obtained during the study, regardless of intercurrent events. All four endpoints are continuous and will be summarized using the number of observations available, mean, SD, minimum, median, and maximum. Mean changes for continuous outcomes will be presented at baseline and at the end of the treatment period (Week 16). Mean (SD) and associated 95% CI, as well as minimum, median, and maximum values will be provided, and the analysis will be tested with 2-sided tests at 5% significance level.

Key Secondary endpoints will undergo hierarchical testing in the order displayed in [Section 4.6](#), using two-sample t-test. The results of the test will be displayed in a summary table.

Missing data handling of key CGM secondary endpoints will follow the same approach as the primary estimand.

Regarding participants who discontinue treatment early, but complete the early termination visit per protocol and have MMTT collected at the EOT visit, their data will be used if collected on study day 56 or later; otherwise, the week 16 outcome will be imputed. If the week 16 MMTT data were collected prior to day 56 or missed, then the week 16 outcome will be imputed using baseline observation carried forward (BOCF).

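### SAP Table 8 closes the non-CGM Week 16 window at Day 116, so a late Visit 7 has no Week 16 meal test, HbA1c or DM-SAT, and its maximum PPG change would most likely be set to zero

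*SAP*

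**What the plan says.** SAP 5.4.5 applies analysis windows broadly: "All post-baseline data (e.g. CGM data, MMTT data, patient reported outcome data, laboratory data, physical exam data, and vital signs data) will use windowing". It adds: "The visit windows will consider nominal visits and unscheduled visits within the window". Table 8, titled for non-CGM data, ends with the row "Week 16 113 103 – 116" (week, target day, days). Day numbering is set in the same section: "Participants are enrolled into the trial at Visit 3.2, which is considered Day 1".

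The rules that decide what happens when a Week 16 value is absent are elsewhere:

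- **Maximum PPG** (SAP 4.4.1.1) needs only a baseline value in the enrolled set. It is third of four in the hierarchy of SAP 4.6.
- **Missing key secondary values** are imputed from baseline (protocol 8.7.3.1). SAP 4.4.1.2 does the same for a Week 16 meal test that was missed or done before Day 56. For early discontinuers who have an end-of-treatment test, "their data will be used if collected on study day 56 or later; otherwise, the week 16 outcome will be imputed".
- **PPG AUC and Tmax** (SAP 4.4.2) and **HbA1c and DM-SAT** (SAP 4.5.1) need both a baseline and a Week 16 value.
- **CGM Week 16** (SAP 4.3.1) opens at Day 95 and has no closing day.

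Before treatment, Table 8 has the row "Week -2 -15 -14 to -1", while the Week -4 row runs "informed consent date to -15". Footnote k of the schedule reads: "Visit 2 will be performed at Day -15 for ALL participants".

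**The concern.** The meal test, HbA1c and DM-SAT have no scheduled post-baseline assessment other than Visit 7. If Visit 7 falls outside the Week 16 row, nothing else can fill the gap. A completer who attends a few days late with a full set of assessments would be handled like someone never assessed. The observed PPG change would give way to an imputed zero in an endpoint that gates the one after it, and the participant would leave the AUC, Tmax, HbA1c and DM-SAT summaries.

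The rules also do not fit together. The same late visit can supply valid Week 16 CGM data, because that window stays open. An early discontinuer's meal test is accepted from Day 56 with no upper limit, although Table 8 puts Days 56 to 60 in Week 8 and Days 61 to 102 in Week 14.

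**Working it through.** **1. Reproduce the table.** Inputs are the schedule days and ± 3-day allowances (protocol 13.1, repeated in SAP 5.4.5), and Visit 3.2 as protocol Day 0 = SAP Day 1. After baseline, SAP day = protocol day + 1.

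| Visit | Protocol day | SAP target | Last allowed SAP day | Table 8 target / close |
|---|---|---|---|---|
| 5 (Week 8) | 56 ± 3 | 57 | 60 | 57 / 60 |
| 6 (Week 14) | 98 ± 3 | 99 | 102 | 99 / 102 |
| 7 (Week 16) | 112 ± 3 | 113 | 116 | 113 / 116 |

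All three rows reproduce. Visit 7 is allowed on Days 110 to 116, all inside 103 to 116. Day 117 is the first day with no row.

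**2. How a Visit 7 can fall on Day 117 or later.**

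- It is held more than 3 days late.
- Visit 6 is on its last allowed day, 102. Removal 14 days later is 102 + 14 = 116 (inside). If the fifteenth day after placement is counted as 15 days later, 102 + 15 = 117 (outside).
- A sensor is reinserted on Day 103 or later and worn for 14 more days: 103 + 14 = 117. Protocol 6.2.1 limits end-of-treatment reinsertion to data that can be captured in the 14-day window. Footnote o of the SAP schedule omits that limit.

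**3. Consequence by endpoint.** With no Week 16 record, maximum PPG keeps the participant and baseline carry-forward gives change = 0. AUC, Tmax, HbA1c and DM-SAT exclude the participant.

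**4. Size.** The documents give no count of late visits. Assume 2%, 5% or 10% of completers, with completers = 100 × (1 − 0.15) = 85:

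- 0.02 × 85 = 1.7, about 2
- 0.05 × 85 = 4.25, about 4
- 0.10 × 85 = 8.5, 8 or 9

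If a proportion p of completers is set to zero, and late and punctual completers respond alike, the completers' contribution to the mean change is multiplied by (1 − p). It therefore shrinks by 2% to 10%.

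**5. Effect on the test.** For k zeros among n, with standardized change d: m = d(1 − k/n); variance v = (1 − k/n)(1 + d²) − m²; t = m / √(v/n). Take n = 100 and, as an illustration only, d = 10/25 = 0.4 (the TIR planning values, since none are given for PPG). With k = 0, t = 4.00. With k = 5, m = 0.38, v = 0.9576 and t = 3.88. With k = 10, m = 0.36, v = 0.9144 and t = 3.76.

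**6. Pre-treatment rows.** Day -15 is not in -14 to -1, and it is in the Week -4 row. Week -2 is the only one of the six rows that excludes its own target. Within Week -4, Visit 1 on Day -28 is 0 days from target and Visit 2 is 13 days from it, so the closest-visit rule keeps Visit 1. Visit 3.1 (Day -1) is labelled Week -2.

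**The case against.** The strongest reply is that the zero is never stated. SAP 4.4.1.2 imputes a test that was missed or done before Day 56, and a completed test on Day 118 is neither. The same section speaks of using measurements obtained in the study, and it already departs from Table 8 for discontinuers. The sentence on nominal and unscheduled visits could be read as limiting only the unscheduled ones. This stands in part: zero change is the likely result of following the windows, not a written instruction. But no SAP rule assigns the late test to Week 16, so the choice is left to the programmer.

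Three stronger readings are tempting, and the documents do not support them:

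- **A threat to a positive claim.** Visits within ± 3 days are never lost, and zeros pull the mean toward no effect. The illustration above moves t only from 4.00 to 3.76 with 10 zeros.
- **Table 8 as the source of accepting Day 56 tests.** That acceptance is a separate, explicit rule for discontinuers' meal tests, and it is not stated for HbA1c or DM-SAT.
- **The Week -2 slip as a loss of eligibility or baseline data.** Windowing is stated for post-baseline data, baseline is the last value before first injection (SAP 4.1), and eligibility is not determined from Table 8. HbA1c is the only central-laboratory value scheduled at Visit 2, so the effect is confined to labels in any by-visit table.

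**Conclusion.** The point holds as a minor, easily corrected gap. Taken literally, Table 8 leaves a Visit 7 on Day 117 or later without a Week 16 meal test, HbA1c or DM-SAT. The most likely handling of maximum PPG is then an imputed zero despite an observed value. The expected distortion is a 2% to 10% shrinkage of the mean PPG change, plus the loss of a few participants from AUC, Tmax, HbA1c and DM-SAT. This rests on the assumed frequency of late visits, on late and punctual completers responding alike, and on Visit 3.2 being Day 1. The Week -2 row is an error of labelling only.

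**What to change.** **Week 16 row.** Keep Day 103 as the start and Day 113 as the target. Extend the row past Day 116 to take in any Visit 7 or end-of-treatment assessment up to end of study, on or off drug, using the one closest to Day 113. Visit 8 is a phone contact with no meal test, laboratory sample or DM-SAT, so it adds no competing values. Leave the SAP 4.4.1.2 rule for early discontinuers in place and state that it takes precedence over Table 8 for the meal test.

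Closing the row at last dose + 1 day would be a mistake. A participant whose last dose is on Day 105 and who attends on Day 113 is inside the row now, but would fall outside a row ending on Day 106. That conflicts with the treatment-policy strategy in SAP Table 3.

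**Pre-treatment rows.** End Week -4 at Day -16, start Week -2 at Day -15, and label Visit 3.1 as Baseline by nominal visit. An earlier cut, such as ending Week -4 at Day -22, would mislabel short screenings, since screening may last less than 2 weeks.

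**Cost.** The change is an edit to Table 8 and one sentence on precedence, with no new data. A few Week 16 values will lie some days past target and can be footnoted.
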